5 STUDY POPULATION

Subjects will have Parkinson's Disease and constipation as defined by the inclusion criteria. Parkinson's Disease will be diagnosed according to the UK Parkinson's Disease Society Brain Bank criteria.

5.1 Number of Subjects in this amendment

Approximately 80 subjects will be randomized to ensure approximately 60 subjects will complete all visits, assuming a 25% early termination rate.

5.2 Selection Criteria

Subjects will be screened for the presence of constipation at baseline according to the Rome IV criteria and other inclusion criteria below. Onset of constipation before or after a diagnosis of Parkinson's Disease will specifically be noted and its duration and severity established. The daily electronic stool diary will be analyzed at the end of the two-week screening period (Visit 2) to establish the presence of constipation. Subjects with less than three CSBMs per week, without the use of rescue medication, will be randomized during Visit 2.

5.3 Inclusion Criteria

The study population is defined as subjects who meet the following criteria:

1. Subjects aged 30-90 years, both genders
2. Subjects must provide written informed consent and be willing and able to comply with study procedures.
3. Subjects must be diagnosed with Parkinson's Disease defined as the presence of at least three of the following cardinal features, in the absence of alternative explanations or atypical features: rest tremor, rigidity, bradykinesia and/or akinesia, postural and gait abnormalities.
4. There are insufficient criteria for Irritable Bowel Syndrome (IBS)

5. Constipation which has been present for approximately 6 months
6. Body mass index (BMI) of 18-40 kg/m²
7. Subjects must fulfill Rome IV criteria for functional constipation which includes 2 or more of the following:
 - a. Straining during at least 25% of defecations
 - b. Lumpy or hard stools in at least 25% of defecations
 - c. Sensation of incomplete evacuation for at least 25% of defecations
 - d. Sensation of anorectal obstruction/blockage for at least 25% of defecations
 - e. Manual maneuvers to facilitate at least 25% of defecations (e.g., digital evacuation, support of the pelvic floor)
8. Self-report of 3 or fewer complete spontaneous bowel movements (CSBMs) per week
9. Loose stools are rarely present without the use of laxatives
10. Subjects must be able to read, understand, and accurately record data into the diary to guarantee full participation in the study.
11. Female subjects must have negative serum or urine pregnancy tests and must not be lactating. For females able to bear children, hormonal (i.e., oral, implantable, or injectable), abstinence, same sex relationships, single-barrier method, or a double-barrier method of birth control must be used throughout the study. A vasectomized partner will be allowed as one in conjunction with another single-barrier method.
12. Female subjects unable to bear children must have this documented in the CRF (i.e., tubal ligation, hysterectomy, or postmenopausal [defined as a minimum of one year since the last menstrual period]). Post-menopausal status will be confirmed by follicle stimulating hormone (FSH) in women less than 60 years of age

5.4 Exclusion Criteria

1. Unable or unwilling to provide informed consent or to comply with study procedures.
2. Diagnosis of secondary constipation beyond that of Parkinson's Disease

3. Review of Screening Diaries indicates either of the following:

- Fewer than 11 days of diary completion and/or
- More than 3 complete spontaneous bowel movements per week based upon the average CSBM rate reported during the Screening Period.

4. A compromised gastrointestinal system which includes:

- Structural, metabolic, or functional GI diseases or disorders
- Acute GI illness within 2 weeks of the screening visit
- History of major GI surgery within 30 days of the screening visit (a history of cholecystectomy, polypectomy, hernia repair or appendectomy are not exclusionary as long as they were performed more than 30 days before the screening visit)

5. Unable or unwilling to withdraw from laxatives, opiates, clonazepam, or any medications which may cause constipation, 2 weeks prior to the dose adjustment period and throughout the rest of the study.

6. Unable or unwilling to withdraw from proton pump inhibitors and antacids at the end of the screening period.

7. Any clinically significant abnormalities on screening laboratories or physical examination requiring further evaluation or treatment.

8. Neurological disorder other than Parkinson's Disease that in the opinion of the investigator might interfere with the conduct of the study.

9. On treatment with intra-jejunal dopamine or carbidopa/levodopa (i.e. Duopa).

10. Subjects starting a new Parkinson's Disease medication or modifying an existing medication within 2 weeks prior to enrollment.

11. Unable to maintain a stable diet regimen.

12. Subjects with a cognitive impairment that preclude them from understanding the informed consent.

13. Subjects placed under legal guardianship.

14. Females who are pregnant or breastfeeding.
15. History of excessive alcohol use or substance abuse.
16. Participation in an investigational drug trial within the month prior to dosing in the present study.
17. Any other reason, which, in the opinion of the investigator, would confound proper interpretation of the study.

5.5 Screen Failures

Screen failures are defined as subjects who consent to participate in the study but are not subsequently randomized to the study drug. Minimal information collected will include informed consent date, baseline subject characteristics, all the eligibility criteria violated, reasons for screen failure, AEs that led to screen failure, and any SAEs; these will be entered in the eCRF.

Subjects who do not meet the criteria for participation in the study (screen failure) may / may not be re-screened.

Any subjects who are re-screened should be assigned the same subject number given at the initial screening.

5.6 Discontinuation Criteria and Early Termination Procedures

Subjects may withdraw voluntarily from participation in the study at any time and for any reason. Subjects may also be withdrawn based on the Investigator's clinical judgment.

This study may be terminated at the discretion of the Enterin, Inc. or of any regulatory agency for reasons including safety and/or efficacy.

When a subject withdraws or is withdrawn before completing the study, the date and reason for withdrawal are to be documented. Subjects who withdraw or who are withdrawn prematurely are to attend an early discontinuation visit, at which time they will complete all assessments as outlined in the Schedule of Events ([APPENDIX 2](#)).

In the event that a subject is withdrawn prematurely due to an adverse event or serious adverse event, the adverse event or serious adverse event will be followed until it resolves or stabilizes, or until it is judged by the investigator to be no longer clinically significant.

5.7 Concomitant and Prohibited Medication

- Preventive laxatives will be discontinued during the screening period. This will include all prescription laxatives, over the counter laxatives and dietary supplements. Throughout the study, subjects will be allowed to take constipation rescue medication on demand, and only if they have not had a bowel movement in three consecutive days. Rescue medications will be recorded in the electronic daily diary every time a laxative is used. Bowel movement produced within 24 hours of rescue medication or accidental self-prescribed laxative use will not be counted as either spontaneous bowel movement or complete spontaneous bowel movement.
- Proton pump inhibitors and antacids will be discontinued at the end of the screening period and reinstated during the wash-out period.
- Barbiturates, and opiates will be discontinued at the end of the screening period and 2-3 days before dosing and reinstated during the wash-out period. All medications shall be reviewed and dis/approved by the investigator on a case-by-case basis.
- Selective serotonin reuptake inhibitor (SSRI), SNRI, tricyclic antidepressant, anti-cholinergic, anti-histaminergic and anti-psychotic agents are permissible at stable doses.
- Dopamine agonists and amantadine will be allowed if on a stable dose for at least 2 weeks preceding the study.
- Deep brain stimulation is allowed if present for more than 6 months and at stable stimulation parameters.

Subgroup Analyses

[figure not shown]
Subjects will be analyzed overall by their randomized treatment assignment (i.e., active versus placebo). Subgroup analyses will also be performed by a subject's baseline CSBM rate (i.e., 0-0.9, or 1.0-3.0). The primary efficacy endpoint and key secondary, exploratory and safety endpoints will be summarized by these subgroups. Additional subgroup analyses may be defined in the statistical analysis plan (SAP).

6.0 MATERIALS**6.1 Study Drug**

All study medication and placebo will be supplied by Enterin, Inc. as 25 mg tablets packaged in white opaque high-density polyethylene (HDPE) bottles with child-resistant closures.

6.2 Packaging and Labeling

Study medication will be shipped to the investigational sites in blinded packaging.

6.3 Storage, Dispensing and Reconciliation of Study Drug and Identity of Investigational Products

All study medication is to be stored at “Controlled room temperature” as defined below.

Controlled room temperature: The temperature maintained thermostatically that encompasses the usual and customary working environment of 20°–25° (68°–77° F). The following conditions also apply. Mean kinetic temperature not to exceed 25°. Excursions between 15° and 30° (59° and 86° F) that are experienced in pharmacies, hospitals, and warehouses, and during shipping are allowed. Provided the mean kinetic temperature does not exceed 25°, transient spikes up to 40° are permitted as long as they do not exceed 24 h. Spikes above 40° may be permitted only if the manufacturer so instructs.

Articles may be labeled for storage at “controlled room temperature” or at “20°–25°”, or other wording based on the same mean kinetic temperature [see also [Good Storage and Distribution Practices for Drug Products \(1079\)](#), [Quality Management System](#), [Environmental Management System](#), [Mean Kinetic Temperature \(MKT\) Calculation](#)].

An article for which storage at Controlled room temperature is directed may, alternatively, be stored and shipped in a cool place or refrigerated, unless otherwise specified in the individual monograph or on the label.

Storage on- site should be in a locked and secure location accessible only to site staff involved with this study. A temperature log must be kept to document temperature which should be recorded at least once each working day. If the temperature is not maintained, the sponsor should be contacted.

If a site becomes aware that study medication has not been properly handled, the sponsor must be contacted immediately. In such an event, study medication should not be dispensed to any subject until the sponsor provides further direction.

Neither the investigator nor any study personnel will distribute any study medication to any person not participating in this study. The study medication will be dispensed at the discretion and direction of the investigator in accordance with the conditions specified in this protocol. It

Commented [A3]: Remaining comment from [name] to be addressed: Do you want to add the requirement to use min/max temperature measuring devise?

We will discuss at Dev team tomorrow

is the investigator's responsibility to ensure that accurate records of study medication issuance and return are maintained.

Enterin is responsible for the tracking and accountability of study medication dispensed to sites and will inform sites how to return or destroy study medication once it is no longer needed at the site.

Table 6.1: Identity of Investigational Products

Active Dosage form	25 mg Tablet	White Tablet
Placebo Dosage form	25 mg tablet	White tablet Identical in appearance but contains no active ingredient

Table 6.2: Route of Administration

Route/dosage	Oral (PO). Doses will require multiple tablets: 75 mg=3 tablets 100 mg=4 tablets 125 mg=5 tablets 150 mg=6 tablets 175 mg=7 tablets 200 mg=8 tablets 225 mg=9 tablets 250 mg=10 tablets
Dosing Instructions	Take 60 min before breakfast with 8 oz. water

7 WARNINGS AND PRECAUTIONS

Subjects will be advised to stay at home for 4-6 hours after taking the first at-home dose of medication in case they need to evacuate urgently. Beyond the first dose, subjects themselves will be in a position to know if and when to leave the house.

8 STUDY PROCEDURES

8.0 Observations and Measurements

Subject informed consent must be obtained prior to conducting any study-related procedures. The Principal Investigator at each center will ensure that the subject is given full and adequate oral and written information about the nature, purpose, possible risk and benefit of the study. Subjects must also be notified that they are free to discontinue from the study at any time. The subject should be given the opportunity to ask questions and allowed time to consider the

information provided. All assessments and procedures will be completed according to the Schedule of Events.

8.1 Instructions to Subjects

Subjects and their spouse/companion will be taught how to fill in the daily diaries for stool and laxative. They will be instructed about the use of rescue medication and told to record it in the diary immediately.

8.2 NCI CTC AEv4.03 Definitions of Dose Limiting Adverse Events

Adverse Event	Grade 1	Grade 2	Grade 3	Grade 4	Grade 5
Diarrhea (watery stool)	Increase of <4 stools a day over baseline	Increase of 4 - 6 stools per day over baseline; moderate increase in ostomy output compared to baseline	Increase of ≥ 7 stools per day over baseline; incontinence; hospitalization indicated; severe increase in ostomy output compared to baseline; limiting self-care ADL	Life threatening complications ; urgent intervention indicated	Death
Vomiting	1-2 distinct episodes per 24 hrs	3-5 distinct episodes per 24 hrs	6 or more distinct episodes in 24 hrs; tube feeding, TPN or hospitalization indicated	Life-threatening consequences ; urgent intervention indicated	Death
Abdominal pain	Mild pain	Moderate pain; limiting instrumental ¹ ADL	Severe pain; limiting self-care ADL ²	-	-
Postural hypotension ³	Mild, transient lightheadedness or dizziness upon rising from	Moderate lightheadedness , dizziness or fainting upon	Severe lightheadedness, dizziness or fainting upon rising from	Life-threatening and urgent intervention indicated	Death

	lying or sitting position that does not interfere with ADL	rising from lying or sitting position that limits instrumental ADL; Non-urgent medical intervention indicated	lying or sitting position that limits self-care ADL; Medical intervention or hospitalization indicated		
--	--	---	--	--	--

¹Preparing meals, shopping for groceries or clothes, using the telephone, managing money, etc.

²Bathing, dressing and undressing, feeding self, using the toilet, taking medications, and not bedridden

³Definition adapted from combining CTCAE definitions for Hypotension and Dizziness

8.3 Criteria for Dose Limiting Toxicity (DLT) Endpoints:

Recurrent vomiting: 3-5 episodes of vomiting within 24 hours of taking study medication/placebo (Grade 2 adverse event)

Recurrent diarrhea: >7 episodes of diarrhea within 24 hours of taking study medication/placebo (Grade 3 adverse event)

Abdominal pain: Moderate pain that limits instrumental activities of daily living within 24 hours of taking study medication/placebo (Grade 2 adverse event)

Dizziness: Moderate lightheadedness or fainting upon rising from lying to sitting or standing and severe enough to require medical intervention within 24 hours of taking study medication/placebo (Grade 2 adverse event) or either a systolic blood pressure less than 80mmHg or diastolic blood pressure less than 40mm Hg.

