Informed Consent	X						
Inclusion/Exclusion Criteria ^a	X	X					
Demographics/Medical History	X						
Complete Physical Exam	X						X
Brief Physical Exam			X	X	X	X	
Height	X						
Weight	X	X	X	X	X	X	X
Orthostatic Vital Signs ^b	X	X	X	X	X	X	X
12-lead ECG	X	X	X	X	X	X	X
Labs and Urinalysis	X		X	X	X	X	X
Pregnancy Testing ^c	X	X	X	X	X	X	X
In-clinic IP/Placebo Dosing ^d			X	X	X		
In-clinic Levodopa Dosing		X	X	X	X	X	X
Levodopa PK Draws ^e		X ^e	X ^e	X ^e	X ^e	X ^e	X ^e
IP/Placebo Dispense		X	X	X			
IP/Placebo Collection and Accountability			X	X	X	X	X

Commented [A1]: Confirm whether +/- 8 days or only +8 days

CONFIDENTIAL

19April21 7.0

	Visit 1 Screening	Visit 2 Randomization	Visit 3 Follow-Up	Visit 4 End of Treatment	Visit 5 End of Placebo	Visit 6 End of Study	Early Termination
	Day -21	Day 1 (+/-8 days)	Day 11 (+/- 3 day)	Day 26 (- 2 days)	Day 39 (+/- 8 days)	Day 69 (+/- 8 days)	
Instructions to Discontinue Laxatives and other BM Medications	X						
Dispense Rescue Medications ^f	X	X	X	X	X		
Stool Diary Instruction/Review ^g	X	X	X	X	X	X	X
AE Review	X	X	X	X	X	X	X
Prior and Con Meds	X	X	X	X	X	X	X
Rome IV questionnaire	X						
MDS-UPDRS ^h	X		X	X	X	X	X
C-SSRS	X	X	X	X	X	X	X
BDI-II	X		X	X	X	X	X
MMSE	X		X	X	X	X	X
SAPS-PD, Hallucination/Delusion Questionnaire ⁱ	X	X	X	X	X	X	X
PAC-QOL and PAC-SYM		X	X	X	X	X	X
Dispense Stool Collection Kits	X		X				
Collect Stool Sample ^j		X		X			X

CONFIDENTIAL**19April21_7.0**

a. Confirmation of eligibility: To be randomized to receive double-blind study medication in this study, subjects must meet the following criteria:

- Have had at least 11 "Available Data Days" (days with electronic diary compliance sufficient for determining whether a BM occurred)
- Have had <3 CSBMs/week based upon the average CSBM rate during the first 2 screening weeks (baseline period).
- Be approved for randomization by the enrollment committee

b. Three sets will be taken. Time points to be defined. Orthostatic vital signs will be taken in the supine position and will include BP and HR, sitting or standing BP and HR, RR, and body temperature. . Sitting or standing measurements will be taken within approximately 5 minutes of sitting or standing.

c. For women of child-bearing potential, on-site with urine pregnancy test kit. If the on-site UPT is positive, a serum pregnancy test will be done. For post-menopausal women <60 years or of age, a serum FSH will be done at the screening visit only.

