3 OBJECTIVES AND ENDPOINTS

3.1 Primary Objective and Endpoints

The purpose of this study is to evaluate the safety, tolerability, and efficacy of repeated oral doses of ENT-01 for up to 25 days in subjects with Parkinson's Disease-related constipation in a randomized, double-blind, placebo-controlled study.

Safety:

The **primary safety objective** of this study will be the evaluation of the safety of repeated daily oral dose of ENT-01 for up to 25 days in subjects with PD-related constipation.

Safety endpoints will include adverse events as evaluated with subject self-reporting, vital signs, clinical chemistry and hematology blood analyses, urinalysis, and electrocardiogram (ECG).

It is anticipated that no more than 2 subjects out of 60 (3.3%) will have an adverse event of grade 4 or 5 that is at least possibly related to ENT-01 in this Study. Should there be more than 2 subjects with an adverse event grade 4 or 5 that is at least possibly related to ENT-01 in the cohort of subjects randomized to ENT-01, the study will be put on an immediate clinical hold.

In addition, individual safety stopping rules will include:

- Reaching dose-limiting tolerability (DLT) before a prokinetic effect
- Having a non-DLT gastrointestinal adverse event > grade 3 within 24 hours of taking study medication or placebo, that is at least possibly attributable to ENT-01
- A fall in systolic blood pressure to < 80 mm Hg upon rising from lying to sitting or standing
- A fall in diastolic blood pressure to < 40 mm Hg upon rising from lying to sitting or standing
- Elevation of liver function tests (LFTs) > 3 times the upper limit of normal(ULN)

Tolerability

The primary tolerability objectives will be evaluation of recurrent vomiting, recurrent diarrhea, abdominal pain and dizziness.

Tolerability endpoints are referred to as the DLT and will include:

- Recurrent vomiting defined as 3-5 episodes of vomiting within 24 hours of taking study medication/placebo
- Recurrent diarrhea defined as 7 or more episodes of diarrhea within 24 hours of taking study medication/placebo
- Abdominal pain defined as moderate pain that limits instrumental activities of daily living (ADL) (e.g., preparing meals, shopping for groceries or clothes, using the telephone, managing money, etc.) within 24 hours of taking study medication /

placebo.

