4.1 Visit 1: Screening Visit (Study days -21 to -1)

The purpose of the baseline or “screening” period is to establish constipation severity off laxatives. At the end of the screening period the subject’s eligibility will be assessed by an

Evaluation Committee.

During Visit 1, the following assessments and procedures will be performed:

- Informed consent
- Inclusion/Exclusion Criteria
- Demographics/Medical History
- Complete Physical Exam
- Height
- Weight
- Orthostatic Vital Signs – 3 sets: Vital signs will include supine blood pressure and heart rate, sitting or standing blood pressure and heart rate, respiratory rate, and body temperature. Sitting or standing measurements will be taken approximately 5 minutes after the subject has been sitting or standing. The sets should be taken throughout the Visit and not sequentially.
- 12-lead ECG
- Labs and urinalysis: as defined in [APPENDIX 1](#).
- Pregnancy Testing – For women of child-bearing potential, this is done on-site with the urine pregnancy kit (UPT) provided. If the on-site UPT is positive, then a serum pregnancy test will be done. For post-menopausal women less than 60 years or age, a serum FSH will be done at the screening visit only.
- Instructions to Discontinue Laxatives and other Constipation medications. All prescription laxatives (Linzess, Amitiza), over the counter laxatives (Miralax, Ex-lax, Bisacodyl/Dulcolax), suppositories (Bisacodyl/Dulcolax), enemas (Fleets), and dietary supplements to increase bowel movements (chia seeds, bran, fiber supplements) will be discontinued.
- Dispense Rescue Medication: Subjects will be provided with suppositories and enemas. Anytime during the study if a subject does not have any bowel movement for three consecutive days, rescue medication should be used to evacuate their bowel as directed by the

site. In the rare event that the above does not produce a bowel movement, the subject will be instructed to notify the site and ask for direction.

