8.15 Stopping Rules

It is anticipated that no more than 2 subjects out of 60 (3.3%) will have an AE of grade 4 or 5 that is at least possibly related to ENT-01 in this Study. Should there be more than 2 subjects with an AE grade 4 or 5 that is at least possibly related to ENT-01 in the cohort of subjects randomized to ENT-01, the study will be put on an immediate clinical hold.

In addition, individual safety stopping criteria will include:

- Having a non-DLT gastrointestinal adverse event > grade 3 within 24 hours of taking ENT-01 that is at least possibly attributable to ENT-01
- A fall in systolic blood pressure to < 80 mm Hg upon rising from lying to sitting or standing

- A fall in diastolic blood pressure to < 40 mm Hg upon rising from lying to sitting or standing
- Elevation of liver function tests (LFTs) > 3 times the upper limit of normal (ULN)

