2.6.6 Tolerability Endpoints

The tolerability endpoint is referred to as the dose limiting toxicity (DLT). These adverse events are considered as DLT:

- Recurrent vomiting defined as 3-5 episodes of vomiting within 24 hours of taking study medication/placebo

- Recurrent diarrhea defined as 4 or more episodes of diarrhea within 24 hours of taking study medication/placebo
- Abdominal pain defined as moderate pain that limits instrumental activities of daily living (ADL) (e.g., preparing meals, shopping for groceries or clothes, using the telephone, managing money, etc.) within 24 hours of taking study medication/placebo
- Dizziness defined as lightheadedness or fainting on rising from lying to sitting or standing that limits instrumental ADL and severe enough to indicate non-urgent medical intervention within 24 hours of taking study medication/placebo.

It is anticipated that all subjects receiving active treatment will exhibit a prokinetic effect at a dose lower than DLT and less than or equal to 250 mg. Subjects reaching DLT before a prokinetic effect will be treated at the highest dose at which they did not experience a DLT.

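### Protocol 8.3 makes a systolic pressure below 80 or diastolic below 40 mm Hg a dizziness DLT, but the SAP tolerability table uses a symptom-only definition and leaves pressure-only events out

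*Protocol*

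**What the plan says.** Protocol 3.1 equates the primary tolerability endpoints with the DLTs: "Tolerability endpoints are referred to as the DLT and will include" four events, one of them dizziness. Its dizziness entry has the same wording as SAP 2.6.6: "Dizziness defined as lightheadedness or fainting on rising from lying to sitting or standing that limits instrumental ADL". Both entries add that the symptoms must call for medical help, though not urgently. Neither place gives a pressure value.

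Protocol 8.3, which sets out the DLT criteria, describes symptomatic dizziness and then adds an alternative: "or either a systolic blood pressure less than 80mmHg or diastolic blood pressure less than 40mm Hg".

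The same two thresholds also appear outside the DLT definitions, as individual stopping criteria in Protocol 3.1, Protocol 8.15 and SAP 2.3. The systolic criterion reads "A fall in systolic blood pressure to < 80 mm Hg upon rising from lying to sitting or standing". A matching diastolic criterion follows it: "A fall in diastolic blood pressure to < 40 mm Hg upon rising from lying to sitting or standing".

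On what follows a DLT, SAP 2.6.6 states: "Subjects reaching DLT before a prokinetic effect will be treated at the highest dose at which they did not experience a DLT". Protocol 3.1 and SAP 2.3 list a DLT before a prokinetic effect among the individual stopping criteria. Protocol 8.15 gives the other criteria but not that one.

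Protocol 9.2.3 and SAP 4.8.10 both summarise the frequency of DLT endpoints by treatment group and dose level, for the Dose Adjustment period only.

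**The concern.** One primary tolerability endpoint has two definitions, and they classify the same subject differently. Take a subject with a systolic reading of 78 mm Hg and no disabling symptoms. Under Protocol 8.3 this is a dizziness DLT. Under Protocol 3.1 and SAP 2.6.6 it is not. If the reading was taken on rising, it is also an individual stopping criterion. The subject could meet a stopping criterion for low pressure and still not be counted in the SAP's tolerability table.

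The SAP does not flag the difference: section 5 states that the planned analyses match the protocol. At stake is whether the tolerability rate reported for a Parkinson's population includes low pressure without qualifying symptoms, and whether sites and analysts would treat a DLT in the same way.

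**Working it through.** No sample size, power or event rate enters this point, so the check is a comparison of the passages.

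| Place | Role | Pressure below 80/40 | Symptoms limiting daily activities required | Only on rising |
|---|---|---|---|---|
| Protocol 8.3 | DLT criteria | Yes, sufficient alone | Not for the pressure limb | Not for the pressure limb |
| Protocol 3.1, tolerability list | DLT definition | No | Yes | Yes |
| SAP 2.6.6 | DLT definition | No | Yes | Yes |
| Protocol 8.2 grading table | Grades of postural hypotension | No | From Grade 2 | Yes |
| Protocol 3.1, Protocol 8.15, SAP 2.3 | Individual stopping criterion | Yes | No | Yes |

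The thresholds agree wherever they appear. What differs is the class (DLT or stopping criterion) and the postural condition.

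Which definition is tabulated:

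- SAP 4.8.10 counts DLT endpoints, and the only DLT definition in the SAP is 2.6.6. Pressure-only events are therefore left out of the SAP table.
- Protocol 9.2.3 counts DLT endpoints without pointing to 3.1 or 8.3, so the Protocol does not settle the matter.
- Events that also meet the symptom definition are counted either way. Only pressure-only events are affected.

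What follows a DLT before a prokinetic effect:

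- SAP 2.6.6: the subject is treated at the highest dose without a DLT. The efficacy text of Protocol 3.1 points the same way, since it lets the Fixed Dose period begin at that dose.
- Protocol 3.1 (stopping rules) and SAP 2.3: it is an individual stopping criterion.
- Protocol 8.15: not listed.

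Which readings can reach the table, from the visit schedule in Protocol Table 1, with Visit 2 as Day 1 and the first dose taken at home the next day:

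- Visit 2 readings precede the first dose.
- Visit 3 is Day 11 ± 3, that is Days 8 to 14, or dosing days 7 to 13.
- Visit 4 is Day 26 with up to 2 days earlier allowed, that is Days 24 to 26, or dosing days 23 to 25.
- With one tablet added every 3 days and no delay, a start at 3 tablets reaches 10 tablets after (10 − 3) × 3 = 21 days, on dosing day 22. A start at 6 tablets reaches it after (10 − 6) × 3 = 12 days, on dosing day 13.

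So Visit 3 normally falls within dose adjustment for a subject not yet on a fixed dose, and Visit 4 normally falls after it. Under SAP 2.5, a subject who stays on one dose throughout has no escalation period, so even a Visit 3 reading would not enter. Apart from early-termination or unscheduled readings, mainly Visit 3 can add a pressure-only DLT.

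A minor point concerns the upright reading itself. Protocol 4.1 says "Sitting or standing measurements will be taken approximately 5 minutes after the subject has been sitting or standing", while footnote b of Protocol Table 1 says "Sitting or standing measurements will be taken within approximately 5 minutes of sitting or standing". The first describes a reading after a period upright; the second allows one immediately on rising.

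**The case against.** Several arguments limit this point, and most of them stand.

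The Protocol's own analysis need not omit these events. Section 8.3 is the section devoted to DLT criteria, and 9.2.3 can fairly be read as using it. A reader might infer that the primary tolerability endpoint misses pressure-only events in both documents. That is firm only for the SAP table.

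The events are not lost. SAP 4.8.6 summarises and lists vital signs by subject, and SAP 4.8.2 tabulates adverse events leading to discontinuation. What is missing is a count of subjects below the thresholds, since no such table is planned.

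Being both a DLT and a stopping criterion is not in itself a contradiction, because Protocol 3.1 and SAP 2.3 make a DLT before a prokinetic effect a stopping criterion anyway. The conflict in handling is narrower: SAP 2.6.6 continues treatment in that situation.

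A reader might also apply an assumed rate to all ENT-01 subjects. For example, 2% to 5% of about 94 (54 + 40) gives 2 to 5 events. The documents give no rate, and the table covers only the Dose Adjustment period, so they do not support that count.

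Nor do they show that change from baseline in pressure mixes postures. Sitting or standing is allowed, but SAP 4.8.6 does not say how upright readings are combined, and the case report form is not available.

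Finally, because a DLT can mark the start of the Fixed Dose period, a reader might carry this through to the efficacy populations. Nothing in the documents shows that any subject's status turns on it, and I make no such claim.

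**Conclusion.** The inconsistency is real and should be corrected. As written, the SAP tolerability table excludes pressure-only events that Protocol 8.3 classes as dizziness DLTs, and SAP section 5 does not declare the difference. Separately, the passages on what follows a DLT before a prokinetic effect conflict within the SAP and within Protocol 3.1, and Protocol 8.15 is silent.

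The number of subjects affected cannot be estimated from the documents and is probably small, because scheduled pressure readings are taken only at clinic visits and mainly those at Visit 3 fall in the tabulated period. This rests on escalation running roughly to schedule and on few unscheduled readings. Safety and tolerability are summarised without hypothesis tests, so the effect is on what is reported, not on an error rate.

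**What to change.** - Use one dizziness DLT definition in Protocol 3.1, Protocol 8.3 and SAP 2.6.6. State whether the pressure limb belongs to it and, if so, whether it applies only on rising. Have Protocol 9.2.3 and SAP 4.8.10 refer to that definition.
- Add one SAP row, by treatment group, for subjects with any systolic reading below 80 or diastolic below 40 mm Hg over the whole Treatment Period, counted whatever action followed. State which readings it uses (all, or upright only). SAP 2.5 starts that period at Visit 2 and ends it the day before Visit 4, so specify readings after the first dose, through and including Visit 4 and any early-termination visit.
- Reconcile Protocol 3.1, Protocol 8.15, SAP 2.3 and SAP 2.6.6 on the handling of a DLT before a prokinetic effect and on the pressure criteria. Which clinical rule should apply is for the sponsor and investigators to settle; this review takes no position.
- As a minor item, give one timing for the upright reading in Protocol 4.1, Protocol Table 1, Protocol Appendix 2 and the SAP schedule. This can only apply to readings still to be taken.

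The cost is document wording and one table row from readings already scheduled. Sites need to be told of the single timing. The reported tolerability rate may look slightly worse.
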